6.2 Objectives

General purpose:

To evaluate the safety and efficacy of the ophthalmic solution PRO-157 in three different posologies versus Moxifloxacin and versus Gatifloxacin in patients with bacterial conjunctivitis.

Specific objectives:

To determine the safety of the PRO-157 solution in three different posologies versus Moxifloxacin and versus Gatifloxacin in patients with bacterial conjunctivitis by the incidence of adverse events and visual capacity.

To evaluate the efficacy of the ophthalmic solution PRO-157 in three different posologies versus Moxifloxacin and versus Gatifloxacin in patients with bacterial conjunctivitis through conjunctival cul-de-sac culture and the clinical evaluation of some ocular signs and symptoms such as: burning, lacrimation, Foreign body sensation, pruritus, photophobia, conjunctival hyperemia, chemosis, secretion, palpebral edema, membranes and / or pseudomembranes, scales and epitheliopathy.

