7 STUDY DESIGN

7.1 Point or limit points

Criteria for the evaluation.

Efficacy measurements:

Main efficacy criterion

Efficacy will be determined by taking cultures of the lower conjunctival cul-de-sac background quantifying (colony-forming units) and identifying genus and basal and final microbial species.

It will be determined as effective if there is a reduction in the number or species of bacterial flora comparing the basal culture against the end between the five different groups of patients and / or if there is a reduction or absence of the following specific signs and symptoms: burning, tearing, Foreign body sensation, pruritus, photophobia, conjunctival hyperemia, chemosis, palpebral edema and secretion, membranes and / or pseudomembranes when comparing the study medication versus Moxifloxacin and versus Gatifloxacin from baseline to final visit.

Efficiency parameters

- The effectiveness of the drug will be evaluated by means of:

1. Clinical referral

2. Microbiological remission

Clinical remission will be evaluated by means of the signs and symptoms that the patient presents at the beginning and at the end of the study.

Variable	Operationalization	Measurement scale	Value
Secretion	Dependent Qualitative ordinal	Absent Present	Must be recorded as absent in 95% of the subjects evaluated
Conjunctival hyperemia	Dependent Qualitative ordinal	Absent Mild Moderate Severe	You must comply with the following: • Absent \geq 95.0% • Mild \leq 5.0% • Moderate \leq 2.5% Severe \leq 1.0%
Chemosis	Dependent Qualitative ordinal	Absent Present	Must be recorded as absent in 95% of the subjects evaluated
Eyelid edema	Dependent Qualitative ordinal	Absent Present	Must be recorded as absent in 95% of the subjects evaluated
Corneal epithelial defects	Dependent Qualitative ordinal	Affected area, percentage	Percentage of affected area less than 95%

The microbiological remission will be evaluated by means of the culture taken from the conjunctival sac fundus.

Variable	Operationalization	Measurement scale	Value
Culture	Dependent Discrete quantitative	UFC * / ml Eradication Reduction Proliferation	Must be recorded as absent in 95% of the subjects evaluated

* Colony forming units

The drugs under study will be considered effective if the patient has any of the following:

1. Clinical remission + Microbiological remission.
2. Clinical referral.
3. Microbiological remission.

Security measurements:

Adverse events and visual capacity.

Evaluation parameters

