• The safety of the use of PRO-157 will be evaluated in the visits indicated in the schedule, through the following parameters:

1. Visual capacity
2. Eye surface
3. Exploration of the previous segment
4. Exploration of the posterior segment
5. Burning
6. Foreign body sensation
7. Lachrymation
8. Conjunctival hyperemia
9. Itching
10. Photophobia
11. Chemosis
12. Tear discharge
13. Eyelid edema
14. Membranes / pseudomembranes
15. Scales
16. Corneal epithelial defects
17. Adverse events

It will be considered that the drug under evaluation is safe for use in humans if there are no changes in the parameters indicated in more than 5% of the subjects, in both eyes, if the

patient goes to all the visits of the study and complies with adherence to treatment $\geq 80\%$ during the time of evaluation of the study.

Variable	Operationalization	Measurement scale	Value
Visual ability	Independent Discrete quantitative	Points logMAR 0-1 0 = Snellen 20/20	Do not present change in 1 line in the Snellen letter or in 1 logarithmic point (log MAR)
Ocular surface	Dependent Qualitative ordinal	Absent Present	Abnormalities in any area of the ocular Surface
Exploration of the previous segment	Dependent Qualitative ordinal	Normal Abnormal	Abnormalities in any of the structures included: cornea, iris, pupil, irido-corneal and crystalline angle.
Exploration of the posterior segment	Dependent Qualitative ordinal	Normal Abnormal	Abnormalities in any of the structures included: vitreous, retina, macula and the optic nerve
burning	Dependent Qualitative ordinal	Absent Present	Must be recorded as absent in 95% of the subjects evaluated
strange body sensation	Dependent Qualitative ordinal	Absent Present	Must be recorded as absent in 95% of the subjects evaluated
tearing	Dependent Qualitative ordinal	Absent Present	Must be recorded as absent in 95% of the subjects evaluated

Secretion	Dependent Qualitative ordinal	Absent Present	Must be recorded as absent in 95% of the subjects evaluated
Conjunctival hyperemia	Dependent Qualitative ordinal	Absent Mild Moderate Severe	You must comply with the following: Absent ≥ 95.0% Mild ≤ 5.0% Moderate ≤ 2.5% Severe ≤ 1.0%
Photophobia	Dependent Qualitative ordinal	Absent Mild Moderate Severe	You must comply with the following: Absent ≥ 95.0% Mild ≤ 5.0% Moderate ≤ 2.5% Severe ≤ 1.0%
Chemosis	Dependent Qualitative ordinal	Absent Present	Must be recorded as absent in 95% of the subjects evaluated

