It is a measure of the ability of the visual system to detect and recognize spatial details, it is performed in a high contrast test and with a good level of illumination. To measure visual acuity (VA) a patient will be presented with different high contrast tests and different sizes at a fixed distance, and the value will be noted as far as the patient sees it. The smallest size that the patient recognizes will be taken as a threshold value and expressed in minutes of arc. Visual ability is the best corrected visual acuity.

Bailey and Lovie designed and proposed a primer that would standardize the answers for each letter size in each of the lines. This was achieved by using a logarithmic progression of the size of the optotypes, obtaining equality in the discernment. They proposed that each line of optotypes contain five letters and the space between them is exactly the size of the letters of the same line and the space between the lines is equal to the size of the optotype of the lower line. In such a way that with this booklet, Bailey and Lovie innovated the method of assessing visual acuity through the logarithm of the minimum resolution angle (logMAR). This type of scale establishes: 1) the visual acuity 20/20 is equal to 0.00 in logMAR and 2) the 20/200 represents in log MAR the unit (1,0). Therefore, each successive line change represents a change of 0.10 logarithmic units. In a line of five letters each letter has a value of 0.02 logarithmic units; in this way, the value of the acuity reached within a line can be objectively annotated. This makes the test have a high degree of reliability. In the area of research, it is called a "Golden Proof".

Standardization of the visual examination:

- At a distance of 3 m in a room with dim lighting, the research subject will be evaluated as follows:
 - This exam will be held at the research center
 - The patient will be asked to always sit in the same place and with the LogMar scale the visual acuity (AV) will be assessed if he / she does not have this type of booklet he / she must carry out the conversion.
 - The research subject will keep both eyes open.
 - The research subject should gently cover one eye with an occluder while reading aloud the smallest line of letters that can be seen. This test is done on each eye, one at a time, starting with the right eye (RE).
 - The doctor must point out, the line that is requested to read the research subject.

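### Visual capacity carries a comparative safety objective, but its only stated criterion is an undirected yes/no change per drug that cannot separate a drug effect from measurement noise, and no comparison of logMAR values between arms is named

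*Combined protocol and SAP*

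**What the plan says.** Section 6.2 sets safety as a comparison of PRO-157, in three posologies, with moxifloxacin and gatifloxacin "in patients with bacterial conjunctivitis by the incidence of adverse events and visual capacity". Section 7.1 lists two security measurements: "Adverse events and visual capacity".

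The safety table in section 7.1 types visual ability as "Independent Discrete quantitative" on a logMAR scale. Its acceptance value is "Do not present change in 1 line in the Snellen letter or in 1 logarithmic point (log MAR". The rule above the table calls the drug safe "if there are no changes in the parameters indicated in more than 5% of the subjects, in both eyes", with further conditions on attendance and adherence.

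Section 17 (Visual acuity) says "each successive line change represents a change of 0.10 logarithmic units" and "In a line of five letters each letter has a value of 0.02 logarithmic units". The procedure itself has the subject "reading aloud the smallest line of letters that can be seen". Offices without a logMAR chart may use their own and convert with a table in 0.1 steps. Infants and uncooperative preschoolers are scored only by whether they perceive and follow light. Acuity is taken on days 1, 3 and 8 (Table 2, section 18.2).

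Section 23 (Analyzed data set) describes each variable in the ITT population and plans an unspecified bivariate analysis in the PP population. It names no test, summary measure or interval for visual capacity.

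**The concern.** The plan has a comparative objective, a quantitative measure and three time points, but the only criterion it writes down reduces each subject to changed or unchanged and judges each drug alone. Acuity varies from test to test, and in this disease it may improve as the infection clears. A count of one-line changes in one arm mixes that variation with any harm. The statement that PRO-157 is as safe for vision as the controls would then rest on a number that does not address the comparison.

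The row also leaves two things open. One line and one logarithmic point are offered as alternatives although they differ tenfold, and no direction of change is given.

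**Working it through.** **Plan's own figures.** None exist for visual capacity. Annex 1 sizes the trial on bacterial eradication only. Its uncorrected values of 135.272 and 36.373 give 147.14 and 43.67 after its continuity correction, in line with the stated 147 and 44 per group.

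**Inputs from the documents.** 60 eyes per arm (sections 1 and 8). One line = 0.10 logMAR and one letter = 0.02 (section 17), so one logarithmic point, 1.0, is 1.0/0.10 = 10 lines. Limit 5% of 60 = 3, so the rule is broken at 4 or more. Two-sided alpha 0.05 (Annex 1).

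**Assumptions.** Normal changes, independent eyes, SD of change 0.05 to 0.10 logMAR, mean loss of two letters = 2 × 0.02 = 0.04 logMAR. Neither the SD nor the clinical weight of a two-letter loss is in the documents. The visual-capacity row is taken alone, with eyes as the denominator.

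**Step 1: the stated rule, one-line change in either direction.** For mean loss m, p = P(change ≥ 0.10) + P(change ≤ −0.10) = 1 − Φ((0.10 − m)/SD) + Φ((−0.10 − m)/SD). The chance of breaking the limit is P(X ≥ 4), with X binomial(60, p). At SD 0.05 and m = 0, p = 2 × (1 − Φ(2)) = 0.046. At m = 0.04, p = 1 − Φ(1.2) + Φ(−2.8) = 0.118.

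| SD | p, no loss | rule broken | p, loss 0.04 | rule broken |
|---|---|---|---|---|
| 0.05 | 0.046 | 29% | 0.118 | 93% |
| 0.06 | 0.096 | 84% | 0.168 | 99% |
| 0.08 | 0.211 | >99% | 0.267 | >99% |

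At SD 0.06 and above, an arm with no mean loss usually fails too.

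**Step 2: other readings of the same row.**
- Loss only: the rule is broken with no mean loss in 5%, 32% and 89% of trials (SD 0.05, 0.06, 0.08), and with a 0.04 loss in 93%, 99% and over 99%.
- Both eyes must change (60 subjects, inter-eye correlation 0 to 0.5): at SD 0.08, 28-63% with no loss and 63-93% with the loss. At SD 0.05, about 0% and 1-22%.
- Threshold of 1.0 logMAR: practically never broken.
- Direction matters. In a simulation with letter-step recording and SD 0.05, both arms were given a common improvement of 0.05 logMAR and PRO-157 a loss of 0.04 against it. The either-direction rule was broken in 72% of PRO-157 arms and in practically all control arms.

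**Step 3: a between-arm comparison, 60 against 60.** The plan does not state one; this shows which summary would serve the objective. For means, power comes from the noncentral t with parameter 0.04/(SD × √(2/60)), which is 4.38, 3.65, 2.74 and 2.19 for the four SDs. For proportions p0 and p1 with average q, power = Φ((|p1 − p0| − 1.96√(2q(1 − q)/60)) / √((p0(1 − p0) + p1(1 − p1))/60)).

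| SD | mean change | loss ≥ 1 line | change ≥ 1 line, either way |
|---|---|---|---|
| 0.05 | 99% | 52% | 30% |
| 0.06 | 95% | 52% | 22% |
| 0.08 | 78% | 43% | 11% |
| 0.10 | 58% | 34% | 6% |

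Exact enumeration of the chi-square test agrees to about one point (53%, 53%, 42%, 34% for loss only).

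**Step 4: sensitivity.** With scores recorded in whole lines (simulation), the powers in the same column order are 92%, 81% and 22% at SD 0.05, and 68%, 51% and 7% at SD 0.08. If two eyes per subject reduce the effective size to 40 or 30 per arm, power on the mean at SD 0.08 falls from 78% to 60% or 48%. At SD 0.12 and 60 per arm, it is 44%.

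**The case against.** A reader might infer that acuity is measured in letters, judged only by the cut, and that a two-letter loss on PRO-157 would therefore be missed in most trials although the data would show it. The documents do not support that.

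- The stated rule is a per-drug limit, not a test between arms. On the one-line reading it flags rather than misses: an arm with a true one-line share of 15% breaks it in 98.5% of trials, one at 10% in 86%, and one at exactly 5% in 35%. Missing the loss is the usual outcome only if the threshold is 1.0 logMAR, or if both eyes must change and the SD is small.
- Letter values are described, but the procedure reads lines and allows conversion in 0.1 steps.
- The cut is the only stated criterion, not the only possible analysis. The variable is typed as quantitative and a bivariate analysis is planned.
- Loss-only proportions have just over 50% power at SD 0.05 to 0.06, and at SD 0.12 the mean also has under 50%.

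All of this stands. It can also be said that a one-line threshold is easy to read, that no visual-capacity hypothesis was powered, and that if only losses count and the SD is 0.05 the rule separates the two cases well (5% against 93%). That depends on a direction and an SD the plan does not give. What the objection leaves untouched is that the objective compares arms and the plan names no comparison of the measured values.

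**Conclusion.** The point holds as a gap in the specified analysis and a defect in the criterion, and should be fixed. The fault of the stated rule is mainly that it does not tell a drug effect from noise. On the either-direction, one-line reading it is broken in 29% to over 99% of trials with no mean loss and in 93% to over 99% with a 0.04 logMAR loss (SD 0.05 to 0.08). If proportions were compared between arms instead, power for that loss would be about 34-53% (loss only) or 6-30% (either way), against 58-99% for the mean (SD 0.05 to 0.10).

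These sizes rest on an assumed SD, normal changes and 60 independent eyes. The advantage of the mean shrinks with whole-line recording, and power falls if subjects contribute two eyes. The documents do not say that a two-letter change matters clinically, so no claim is made that it does. The tenfold mismatch in threshold and the missing direction rest on the text alone and need no assumption.

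**What to change.** In sections 7.1 and 23:

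- Analyse change in logMAR from day 1 to day 8, and to day 3, for each PRO-157 posology against each control. Adjust for baseline logMAR and account for two eyes per subject, for example with a mixed model or clustered standard errors. Report the mean differences with 95% confidence intervals. These are 3 × 2 = 6 comparisons per time point. They are estimates, since the plan sets no margin for visual capacity.
- Keep the count of one-line changes by arm as a supporting table.
- Tabulate separately the children scored only by light following; they have no logMAR value.
- Reconcile one line with one logarithmic point, and state whether improvement counts as change.
- State whether the 5% limit applies to eyes or subjects, and what the reference to both eyes requires.

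The cost is protocol wording and one extra model on data already collected. A mean can hide isolated large losses, which is why the table stays.

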The pathogenesis usually involves the disruption of the ocular surface defense mechanisms, due to trauma, tear film dysfunction or palpebral abnormalities, etc.

Usually its installation occurs 1 to 2 days after contact, characterized by rapid appearance of clinical signs such as palpebral edema, hyperemia, mucopurulent secretion, membranes and / or pseudomembranes.

The main infectious agents in adults are *H. influenzae*, staphylococci and streptococci. *H. influenzae*, *S pneumoniae*, and *Moraxella catarrhalis* are the most frequent agents in children. The course of the clinical picture is 7 to 10 days long.

Due to its clinical presentation, it is convenient to divide them according to their installation time, in acute, acute or chronic hyperinflation, and can guide diagnostic tests and empirical treatment according to the time of presentation.

Common pathogens according to the time of evolution

Acute	Híper Acute	Chronic
Staphilococcus Aureus.	Neisseria Gonorreae.	Moraxella catarrhalis.
Streptococcus pneumoniae.	Neisseria meningitidis.	Moraxella Lacunata.
Haemophilus influenzae.		Enterobacterias.

Special conditions:

In sexually active subjects who do not give up the clinical picture with empirical treatment (ceftriaxone 1gr b.i.d), we should investigate *Chlamydia Trachomatis* and add the relevant treatment.

In the case of infants or minors (less than 2 years old), we should consider granting systemic treatment because 50% of them concur with infections in other systems.

In oculo-vaginal infections we must investigate on strains compatible with trachoma (A-C); since we must remember that it affects more than 40 million subjects in areas of poor hygiene and continues to be a leading cause in non-reversible blindness.

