5 CLINICAL STUDIES

A phase I clinical study was conducted to evaluate the safety and tolerability of the PRO157 ophthalmic solution in healthy volunteers. The tolerability was determined by the presence of: burning, hyperemia, chemosis, foreign body sensation and lacrimation. Safety by assessing visual acuity and / or visual capacity, fluorescein staining, green lysine and intraocular pressure and the frequency of adverse events. A total of 5 visits were made.

- Visit 0: Basal, day 0 (selection period).
- Visit 1: Follow-up, day 2 (treatment period).
- Visit 2: Follow-up, day 4 (treatment period).
- Visit 3: Follow-up, day 7 (treatment period).
- Visit 4: Final day 11 (final visit).

During which time the drop was applied 4 times a day in both eyes, the results that were obtained determined that the variables that reflect tolerability of the product, such as ocular burning, red eye, conjunctival hyperemia and lacrimation, remained predominantly in a low intensity (mild). There was no presence of chemosis or secretion. More than 88% of the eyes studied showed no sensation of a foreign body in the eye and more than 70% of the eyes did not present pruritus in the different evaluations. Variables that reflect the safety of the product, such as visual capacity and intraocular pressure, were always within normal parameters. No findings were reported during the revision of the anterior segment or the posterior segment, none of the eyes studied showed any degree of fluorescein or green lysine uptake in the corneal surface, there were no reports of adverse events. Vi

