8 STUDY PLAN

This is a phase II, randomized, double masked, multicentre, national study.

This study will be carried out with 60 eyes with diagnosis of bacterial conjunctivitis, by treatment group, of patients of the ophthalmological consultation.

Patients diagnosed with bacterial conjunctivitis (signs and / or symptoms and / or culture) recruited will be treated for 7 days with any of the three posologies of PRO157, Moxifloxacin, or Gatifloxacin. The randomization of any of the medications will be coordinated by a member of the research team previously designated who will not be masked and will be responsible for indicating to the patients how to apply the drops, emphasizing the patients of by no means mentioning the evaluating physician with the frequency who applies the study medication.

No patient may use the aforementioned treatment more than the prescribed time. For purposes of the protocol, the infected eye (s) will be taken into account at baseline but the study medication and procedures will be applied and will always be done in both eyes to protect the healthy eye and the possibility of infection if Do not be infected from the beginning.

The study is divided into the following periods:

There will be a total of 3 visits which are divided into 1 baseline visit (day 1) 1 treatment visits (day 3), 1 final visit (day 8). A telephone call will finally be made to evaluate adverse events after 15 days of the last application of medication (day 23)

At each visit from the baseline a clinical photograph of the eyes will be made, each of them must be identified by patient and visit number and delivered once the 30 patients are completed on a CD or USB.

1. Period of treatment of 7 days (from day 1 to 7) where any of the following posologies are applied according to randomization:

PRO157 1 drop 2 times a day in both eyes.
PRO157 1 drop 3 times a day in both eyes.
PRO157 1 drop 4 times a day in both eyes.
Moxifloxacin 1 drop 3 times a day in both eyes
Gatifloxacin1 drop 3 times a day in both eyes

The study medications will be delivered by a coordinator (not blinded) or a person previously designated by the principal investigator, who will indicate how to apply the study medication according to the randomization and will place special emphasis on not mentioning the principal investigator or designee. perform the evaluations as the drop or any characteristic of the jars is applied.

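### Ten conjunctivitis signs carry an absolute 95%-absent safety limit with no reference to baseline, visit or eye status, so infection that has not cleared counts against safety

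*Combined protocol and SAP*

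**What the plan says.** Section 7.1 lists 17 safety parameters. Items 5 to 16 match the twelve signs and symptoms that section 6.2 names for efficacy, which is to be assessed "through conjunctival cul-de-sac culture and the clinical evaluation of some ocular signs and symptoms" (reading the tear-discharge item as secretion, the name used in the table).

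In the safety table:

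- Burning, foreign-body sensation, tearing, secretion, chemosis, eyelid edema, membranes and scales are scored absent or present, with the limit "Must be recorded as absent in 95% of the subjects evaluated".
- Conjunctival hyperemia and photophobia are graded: at least 95% absent, at most 5% mild, 2.5% moderate and 1% severe.
- Itching has no row, and corneal epithelial defects have an area rule.

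That makes 8 + 2 = 10 signs with a 95%-absent limit. The sentence above the table calls the drug safe "if there are no changes in the parameters indicated in more than 5% of the subjects, in both eyes", given attendance at all visits and at least 80% adherence. Safety "will be evaluated in the visits indicated in the schedule", which for ocular signs means days 1, 3 and 8.

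The efficacy part of 7.1 says "Clinical remission will be evaluated by means of the signs and symptoms that the patient presents" at the start and end of the study. Its table sets the same limits for secretion, hyperemia, chemosis and eyelid edema.

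Section 8 adds that "the study medication and procedures will be applied and will always be done in both eyes to protect the healthy eye".

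**The concern.** Patients enter because they have, or are suspected of having, these signs. Section 4.1 describes bacterial conjunctivitis as "characterized by rapid appearance of clinical signs such as palpebral edema, hyperemia, mucopurulent secretion, membranes and / or pseudomembranes". A limit on the share of subjects with the sign, without regard to whether it was there at baseline, mixes two quantities: infection that has not cleared and irritation caused by the drops. For the four signs shared with the remission table, the safety test and the cure test are the same test.

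The problem is clearest for secretion and chemosis. In healthy phase I eyes given four drops a day, section 5 reports "There was no presence of chemosis or secretion", so in this trial those signs more probably come from the disease. It is weaker for burning, tearing, foreign-body sensation and hyperemia, which the drop may itself cause.

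At stake is the tolerability reading of 2, 3 and 4 drops a day. A missed limit may mean slow cure, and a met limit may mean good cure. Neither says much about irritation.

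**Working it through.** **The plan's own figure.** The plan gives no calculation behind the 95% limit. Its sample-size section concerns bacterial eradication: 147 and 44 per group, against 148 and 44 when recomputed with the continuity correction. It supplies no rate of residual clinical signs, so the rates below are assumptions shown as a range.

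**Inputs.** There are 60 eyes per group (summary and section 8) and the limit is 95% absent (7.1). With 60 subjects, 0.05 × 60 = 3, so at most 3 may have the sign.

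**Chance that a non-irritating drug meets the limit for one binary sign.** Let r be the share of subjects whose sign has not cleared, with subjects independent. Then P(meet) = P(X ≤ 3), X ~ Binomial(60, r). At r = 0.10 the terms for 0, 1, 2 and 3 subjects are 0.0018 + 0.0120 + 0.0393 + 0.0844 = 0.137.

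| Assumed residual rate r | P(meet limit) |
|---|---|
| 2% | 0.968 |
| 3% | 0.894 |
| 5% | 0.647 |
| 10% | 0.137 |
| 20% | 0.001 |

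**Subjects versus eyes.** The limit is per subject but groups are counted in eyes, so 60 eyes may be 30 to 60 subjects. With at most floor(0.05n) allowed, P(meet) over that range runs from 0.41 to 0.68 at r = 5% and from 0.06 to 0.22 at r = 10%.

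**Graded signs.** For hyperemia and photophobia, 0.025 × 60 = 1.5 allows at most 1 moderate case, and 0.01 × 60 = 0.6 allows no severe case. These limits are stricter than the binary one, so the table applies to the eight binary rows only.

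**Attribution.** If irritation at rate d and residual disease at rate r act independently, the share with the sign is 1 − (1 − d)(1 − r).

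- d = 0, r = 0.10: share 0.100, P(meet) = 0.137.
- d = 0.05, r = 0.05: share 1 − 0.95 × 0.95 = 0.0975, P(meet) = 0.151.

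A drug that irritates nobody and one that irritates 5% get nearly the same answer.

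**With a new-onset rule.** Residual disease drops out of the count. With 60 subjects at risk and a limit of 3, P(meet) is 0.997 at a new-onset rate of 1% and 0.968 at 2%. Section 7.1 scores the eight binary signs without severity, so new onset can be read from them but worsening cannot.

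**The case against.** The strongest reply is that these limits are secondary. The headline safety measures in 6.2, 7.1 and 18.1 are adverse events and visual capacity. The objective in 6.2 compares arms, and randomisation should spread residual infection across them. New and worsening signs are already adverse events (20.1). Non-improvement is a ground for elimination (15.2), and the rule assumes full attendance and at least 80% adherence, so fewer unresolved eyes may be judged. Several of the signs were phase I tolerability measures, so listing them under safety is legitimate.

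Most of this stands and keeps the point modest. It does not repair the limit, which is absolute and has no comparator term. Elimination for non-improvement is left to judgement, partial improvement still leaves a sign, and data from withdrawn patients are kept for safety (15.3). The sentence in 7.1 that declares the drug safe still rests on the listed parameters.

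A reader might infer something stronger: that the sentence about changes and the table contradict each other, so that healing itself breaches the safety rule. The documents do not support that. Sentence and table can be read as one rule, with the table saying what counts as a departure. Counting healing as harm would go against the efficacy part of 7.1, where reduction of the same signs is success. The sentence also refers to both eyes, so clearing of a one-eyed infection would not obviously qualify. Translation may explain some of the wording. What remains is that the sentence gives neither a direction nor a reference time.

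**Conclusion.** The point holds as a defect in a supplementary safety criterion. As written, the ten limits can fail a drug that irritates no eye, and for secretion, hyperemia, chemosis and eyelid edema they repeat the remission criterion.

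The size depends wholly on the residual-sign rate. The problem is negligible at 2% (0.97), material at 5% (0.65) and near-certain failure at 20% (0.001), for one binary sign in 60 independent subjects. The documents do not place the trial within that range.

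It would be wrong to conclude that the trial cannot assess safety: adverse events and visual capacity do not depend on these limits. The correction is worthwhile because it is cheap and replaces a rule that can give the wrong answer.

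**What to change.** In section 7.1:

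1. Define a safety change as a sign or symptom new or worse than baseline in either eye. State that improvement is not a change, and name days 3 and 8.
2. Tabulate these changes by arm and by baseline eye status (infected or clinically uninfected). For the eight binary signs, report new onset among eyes without the sign at baseline, and rely on adverse-event recording (20.1) for worsening.
3. Remove the 95%-absent limits from the safety decision in infected eyes. Leave the remission limits for secretion, hyperemia, chemosis and eyelid edema as they are. The other six signs have no remission limit. Report persistence of all ten signs descriptively, by arm against the active controls.
4. Use one hyperemia scale with an absent grade. Section 7.1 has one, but the scale in section 17 starts at very mild. State the photophobia grading in section 17 as well.

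**Cost.** The change needs protocol and SAP wording, descriptive tables and the scale correction. No visits, samples or examinations are added, since section 18.2 already records the signs at baseline and on days 3 and 8. If the case report form does not record symptoms by eye, it needs that field.

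**Downsides.**

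- New-onset denominators shrink. If half of 60 eyes have the sign at baseline, 30 remain, and zero events leave a 95% upper limit of 1 − 0.025^(1/30) = 11.6%.
- If the 60 eyes are infected eyes and a share u of subjects have one-eyed infection, uninfected fellow eyes number 60u/(2 − u) per arm. At an assumed u = 0.5 that is 20, and zero events leave an upper limit of 1 − 0.025^(1/20) = 16.8%.
- Irritation that prolongs a baseline sign is seen only in the descriptive arm comparison.
- New onset may still be progression in an infected eye, or spread in a fellow eye.

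These tables describe; they do not test.
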